3.8 Justification of Choice of Study Population

Depressive disorders already emerge in childhood and adolescence, but no pharmacological treatment with antidepressant medication is approved in Switzerland. All prescribed treatments are “off label”. There is some evidence that in particular adolescents respond with an increase in suicidal ideation in the early phase of SSRI treatment. There is a need for novel treatment as the treatment with cognitive behavioural therapy might not always be feasible or sufficiently effective. Omega-3 fatty acids in adults have shown some beneficial effects in MDD, however, so far only small scale RCTs have been performed. Even so meta-analyses have shown moderate effect sizes in adults, results may not be directly transferrable to paediatric MDD given the bigger brain plasticity and the underlying on-going major developmental processes, as described above (see chapter 3.4.3). Therefore, the inclusion of minors is necessary. Participation in the study is preceded by counselling by the treating doctor / psychologist or investigator, during which the minor and its legal representative/parents are informed about the nature and entire course of the study. Age-adjusted patient information sheets for adults and for minors are available. Informed consent will be sought at the same time by the minors themselves and their legal representatives/ parents. The explicit wish of a minor who is capable of forming an opinion and assessing this information to refuse participation will be followed; in such case, the minor can be withdrawn from the study at any time. If a minor subject does not want to participate, they will not be included in the study. This is also explicitly stated in the patient information sheet.

4 STUDY OBJECTIVES

4.1 Overall Objective

The key research question is if omega-3 fatty acids rich in EPA are an effective and safe treatment for pMDD. In addition, we want to investigate if inflammatory mediators, LC-PUFAs and their bioactive lipid markers are response predictors for omega-3 fatty acids treatment or not. Furthermore, we want to investigate if LC-PUFAs and bioactive lipids are associated with particular phenotypic characteristics, e.g. suicidal ideation, impulsivity, cognitive impairment, symptom severity and illness course. Finally, we want to establish a tissue repository (BioBank) in accordance with the HFG/KlinV/HFV.

4.2 Primary Objective

Our primary objective is to investigate the therapeutic efficacy of omega-3 fatty acids in pMDD (WH 1).

4.3 Secondary Objectives

Our secondary objective is to demonstrate a clinical meaningful effectiveness of omega-3 fatty acids (WH 2a-d). Furthermore, we want to investigate immune-modulatory markers, Lc-PUFAs and their bioactive lipids and inflammatory mediators (e.g. cytokines) as predictors for Omega-3 fatty acids treatment response (WH 3a-c). Additionally, we want to investigate if phenotypic characteristics (e.g. suicidal ideation, impulsivity, aggression, anhedonia, hopelessness, cognitive impairment and illness course) are associated with particular LC-PUFAs or their bioactive lipids (WH 4a-d).

Finally, we want to establish a Biobank of this phenotypically well-characterized pMDD sample with longitudinal outcome data that will be made available for future research in accordance with the Swiss HFG/KlinV/HFV.

4.4 Safety Objectives

Our safety objectives are to investigate if Omega-3 fatty acids have an impact on suicidal ideation (in particular because to the reported increased suicidal ideation in association with SSRIs), and is well tolerated in children and adolescents (WH 5a).

5 STUDY OUTCOMES

5.1 Primary Outcome

WH 1 – Based on the findings of Omega-3 fatty acids treatment studies in adult MDD [161, 163, 166], and one small RCT in prepubertal children [167], we assume that we will find a Treatment x Time interaction for the CDRS-R total score in pMDD in favour for Omega-3 fatty acids treatment. The recovery and remission rate based on the structured clinical interview (K-SADS-P) in conjunction with a CDRS-R total score ≤ 28 , as well as the response rates (a 30% decrease in total baseline CDRS-R score after the placebo-lead-in week as proposed by Emslie et al [206]) will be higher in the Omega-3 fatty acids compared to the placebo group at week 12 (response, remission rate) and 36 (recovery, remission rate).

5.2 Secondary Outcomes

WH 2a – We hypothesize that more pMDD patients in the placebo group will be put on antidepressant medication compared to the Omega-3 fatty acids group.

WH 2b – We hypothesize that the Omega-3 fatty acids group will achieve a higher level of functioning (a higher CGAS score) and a better quality of life (overall and within the five dimensions as assessed with KIDscreen-CAT -27) compared to the placebo group.

WH 2c – We hypothesize that the Omega-3 fatty acids group will spend fewer days in hospital and will have a lower outpatient service use (measured with the attrition check list) compared to the placebo group also resulting in a reduction in overall costs (calculated via TARMED points).

WH 2d – We hypothesize that the overall retention rate will be higher in the Omega-3 fatty acids group compared to the placebo group (or, in other words the placebo group will have more and earlier drop outs due to lack of efficacy). This hypothesis will be tested by two means: 1.) in the ITT sample independent if they received an antidepressant in the due course of the trial, as well as 2.) in a modified ITT sample, where those subjects that are put on an antidepressant will be considered as drop-outs from the day they received the first dose of an antidepressant.

WH 3a – Based on the recent meta-analysis [62] showing increased inflammatory mediators in adult MDD, we assume that at least 50% of participants will have a baseline increase of inflammatory mediators (in particular hsCRP, IL-1, IL-6) and a decrease of anti-inflammatory markers (IL-10). Based on a recent Omega-3 fatty acids treatment study in adult MDD [63], we hypothesize that Omega-3 fatty acid response will be predicted by the ratio between pro- and anti-inflammatory markers.

WH 3b – Based on the meta-analysis by Lin et al [54] as well as the study of Potalla et al [61] in pMDD, we hypothesize that about 80% of participants with pMDD will have a reduction in red blood cell Omega-3 fatty acids content, in particular EPA and DHA (used to calculate the Omega-3 index® [207, 208]). We hypothesize that those with an omega-3 index® <4 at baseline will benefit more from Omega-3 fatty acids treatment, whereas those with an omega-3 index >5 (approx. 20%) will not show a marked benefit from Omega-3 fatty acids treatment. We further hypothesize that a high n-6/n-3 Omega ratio at baseline will be associated with a better response to Omega-3 fatty acids.

WH 3c – We hypothesize that low levels of direct metabolites of EPA, in particular HETEs and the E-series-resolvins (RvE1 & 2) will be a strong predictor of Omega-3 fatty acids response.

WH 4a – Based on the meta-analysis of Lin et al [54], we hypothesize that severity of depressive symptoms will be associated with a pro-inflammatory state, as well as an increase in omega-6/3 ratio and a decrease in omega-3 index. Normalization of these parameters will correlate with improvements in depression scores (CDRS-R, DIKJ).

WH 4b - Based on the study by Huan et al [52], we assume an inverse correlation between Omega-3 fatty acids and suicidal ideation (SIQ-Jr), in particular high levels of EPA will protect against suicidal ideation.

WH 4c – Based on the study by Beier et al [209] we assume that low Omega-3 fatty acids, in particular low EPA levels (and a low omega-3 index) will be associated with affect dysregulation, impulsivity/ emotionality (IES-27) and overall psychopathology.

WH 4d – Based on Kiecolt-Glaser et al [205], we hypothesize that high levels of overall stress (as measured with the PSS scale) will correlate with low levels of Omega-3 fatty acids, a pro-inflammatory state, increased saliva cortisol, and high levels of PUFAs oxidation products as

measured by F2 Isoprostanes in the urine and be inversely correlated with the Conner-Davidsons Resilience Scale.

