ALA	Alpha-Linolenic Acid
ALAT	Alanine Transaminase
ANT	Amsterdam Neuropsychological Tasks
aMDD	Adult Major Depressive Disorder
APA	American Psychological Association
ASAT	Aspartate Transaminase
ASEC	Antidepressant Side Effect Checklist
ASR	Annual Safety Report
AWMF	Arbeitsgemeinschaft der Wissenschaftlichen Medizinischen Fachgesellschaften
BAI	Beck Anxiety Inventory
BDI	Beck Depression Inventory
BHS	Beck Hopelessness Scale
BL	Basel -Land
BPD	Borderline Personality Disorder
BRIEF	Behaviour Rating Inventory of Executive Function
BS	Basel-Stadt
CA	Competent Authority (e.g. Swissmedic)
CAM	Complementary Alternative Medicine
CBCL	Child Behaviour Checklist
CBT	Cognitive behavioural therapy
CDI-2	Children's Depression Inventory
CD-RISC	Connor-Davidson Resilience Scale

CDRS-R	Children's Depression Rating Scale-revised
CEC	Competent Ethics Committee
CGAS	Children's Global Assessment of Functioning
CGI	Clinical Global Impression rating scale
CGI-I	Clinical Global Impression rating scale-improvement
ClinO	Clinical Trials Ordinance
CRF	Case Report Form
CRH	Corticotropin-releasing Hormone
CSF	Cerebrospinal Fluid
CTC	Clinical Trials Centre
CTQ-SV	Childhood Trauma Questionnaire-Short Version
D2	Dopaminreceptor 2
DHA	Docosahexaenoic acid
DNA	Desoxyribonuclein acid
DM	Data Management
DSM-IV	Diagnostic and Statistical Manual of Mental Disorders-4th edition
EBPI	Epidemiology, Biostatistics and Prevention Institute
ECNP	European College of Neuropsychopharmacology
eCRF	Electronic Case Report Form
EFAs	Essential fatty acids
EPA	Eicosapentaenoic acid
EPS	Extrapyramidal-motorische Störung
ES	Effect Size
FDA	Food and Drug Administration (USA)
FFQ	Food Frequency Questionnaire
fMRI	Functional Magnetic Resonance Imaging
GC	Gas Chromatography
GCP	Good Clinical Practice
HETE	Hydroxyeicosatetraenoic Acid
HFG	Humanforschungsgesetz
HFV	Verordnung über die Humanforschung mit Ausnahme der klinischen Versuche
HoNOSCA	Health of the Nation Outcome Scales for Children and Adolescents
HPA	Hypothalamic-pituitary-adrenal

hsCRP	High-sensitivity C-reactive Protein
ICD-10	International Classification of Diseases- 10th edition
ICH	International Council on Harmonization
ICH-GCP	International Conference of Harmonisation- Good Clinical Practice
IDMC	Independent Data Monitoring Committee
IEPA	Early Intervention in Mental Health
IES-27-J&E	Jugend- & Elternfragebogen über impulsives Verhalten und Erleben
IFN	Interferon
IICT	Investigator Initiated Clinical Trials
IL	Interleukin

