- Furthermore, we plan to reanalyze the IIT sample according to the PUFA baseline status. In particular we want to compare participants with a omega-3 index <3 compared to those with an omega-3 index $>3/5$ or 8, as increasing evidence suggest that in particular those with a low omega-3 index may benefit from omega-3 supplementation.
- Furthermore, we plan to investigate the influence of inflammatory mediators as response predictors [63].
- Finally we will reanalyze the ITT sample using compliance data (pill count, rbc EPA/DPA change levels, MARS score) to compare fully compliant study participants with partially compliant and non-compliant patients.
- More exploratory will be the analysis of EPA metabolites (HETE; E-series resolvins, prostaglandine, leukotriene) that will be measured in the context of a PhD project as potential predictors of omega-3 fatty acid response.

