11.4.3 Secondary Analyses

Important CDRS-R-related outcome measures include response and remission. Remission is defined as a CDRS total score <28 and response is defined as a 30% drop in CRDS total baseline score (post placebo lead in). Participants using additional antidepressants, days on trial before the additional antidepressant, KIDscreen-CAT-27, and DIKJ will also be analyzed. Supportive endpoints include the number of days in the hospital and the amount of outpatient service use. For analysis details related to secondary and supportive outcomes of the primary trial reporting, please see the separate Statistical Analysis Plan document.

For further secondary outcomes, we will apply the same statistical strategy as for the primary outcome measures. Analysis will include changes in overall and subscores of the in chapter 9.2 listed secondary outcome instruments. We will analyze CDRS-R subscores, DIKJ, BHS, BAI, SIQ-Jr, IES-27, KIDscreen-CAT-27, PSS-10, and Resilience Scale scores and compare them between the treatment groups.

Furthermore, we'll run the following analyses to test our secondary working hypotheses:

- **WH3a:** We will test the effect of inflammatory mediators on the efficacy of omega-3 treatment by introducing an additional continuous factor (ratio between pro- and anti-inflammatory markers) into the linear regression model described in 11.4.2.
- **WH3b:** We will calculate an omega-3 index based on red blood cell Omega-3 fatty acids content and introduce an additional binary factor (n-6/n-3 Omega ratio < 3 vs. n-6/n-3 Omega ratio > 5) into the linear regression model described in 11.4.2.
- **WH3c:** We will test whether direct metabolites of EPA are a strong predictor of Omega-3 fatty acids by introducing additional continuous factors (levels of HETEs and E-series-resolvins at baseline) into the linear regression model described in 11.4.2

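### WH 3c tests HETEs as EPA metabolites, but the protocol's own abbreviation list makes HETE a tetraenoic and EPA a pentaenoic acid, so one of the two named marker families does not match the hypothesis

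*Protocol*

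**What the plan says.** Protocol Section 5.2 words WH 3c as follows: "We hypothesize that low levels of direct metabolites of EPA, in particular HETEs and the E-series-resolvins (RvE1 & 2) will be a strong predictor"; what is to be predicted is response to omega-3 treatment. Two marker families are named, and both are presented as coming directly from EPA.

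The same classification appears twice in the statistical section. Section 11.4.1 plans an "analysis of EPA metabolites (HETE; E-series resolvins, prostaglandine, leukotriene") as potential response predictors, describes this as one of the more exploratory parts, and places it in a PhD project. Section 11.4.3 tests WH 3c by adding "additional continuous factors (levels of HETEs and E-series-resolvins at baseline") to the regression model of Section 11.4.2.

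The abbreviation list expands HETE as "Hydroxyeicosatetraenoic Acid" and EPA as "Eicosapentaenoic acid". It gives no parent fatty acid for HETE.

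Section 9.2.2.4 has the predictive markers other than hsCRP measured from stored blood after the last patient's final visit, with an exception for baseline data used in add-on projects. The synopsis names LC-MS/MS as the method for the bioactive lipids and gives the E-series resolvins only as an example. SAP Section 2 moves the lipid-marker analyses to later analysis plans.

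**The concern.** WH 3c is about how much EPA is being turned into its active products at baseline. The markers that stand for this should be products of EPA. By name, the HETEs are not its simple hydroxy products, because the two names carry different numbers of double bonds.

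What is at stake is the reading of a listed secondary hypothesis. If HETE levels turn out unrelated to response, the plan's labels would have this reported as EPA metabolites failing to predict response. If they turn out related, it would be reported as support for, or evidence against, an EPA mechanism. Neither sentence would be justified by a marker whose link to EPA the protocol never shows.

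**Working it through.** There is no figure to reproduce: neither document gives a power, effect size or sample size for WH 3c. The check is textual.

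**Inputs**

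| Item | Where | Content |
|---|---|---|
| EPA | Protocol, abbreviations | eicosa-**penta**-enoic: 20 carbons, 5 double bonds |
| HETE | Protocol, abbreviations | hydroxy-eicosa-**tetra**-enoic: 20 carbons, 4 double bonds |
| WH 3c | Protocol 5.2 | HETEs and E-series resolvins both called direct EPA metabolites |
| Exploratory predictor list | Protocol 11.4.1 | HETE placed first among "EPA metabolites (HETE; E-series resolvins, prostaglandine, leukotriene") |
| WH 3c model | Protocol 11.4.3 | HETE and resolvin levels enter as continuous factors |
| Test rule | Protocol 11 | two-tailed, 5% |

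**Step 1, naming.** The hydroxy prefix records an added hydroxy group and leaves the count of double bonds as it was. Applied to EPA, the count stays at 5, and the product is a hydroxyeicosapentaenoic acid (HEPE). A HETE has 4, so 5 − 4 = 1 double bond is unaccounted for. The class that WH 3c names is not the one that its stated parent would give.

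**Step 2, whether the protocol resolves this elsewhere.** It does not. Sections 5.2, 11.4.1 and 11.4.3 repeat the classification without a reason. Section 3.1.3 says that arachidonic acid, an omega-6 acid, and EPA and DHA, which are omega-3 acids, each have metabolites, but places HETE under none of them. The pathway figure cited there was not available in the text reviewed.

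**Step 3, extent.** The mismatch affects 1 of the 2 marker families in WH 3c and in Section 11.4.3, and 1 of the 4 classes in Section 11.4.1 (HETE, E-series resolvins, prostaglandins, leukotrienes).

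**Step 4, effect on the test.** Each marker is a continuous factor tested two-sided at 5%. The test of a HETE coefficient has the same alpha whatever the marker is called. What changes is the conclusion that may be drawn from it.

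**The case against.** The best defence is that the abbreviation list only spells out names, that no sentence in either document says where HETEs come from, and that three sections consistently call them EPA metabolites. It is true that no parent is stated. But those three sections are the statements in question, so their agreement is not evidence that they are right, and the naming argument needs no statement about any other parent acid.

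The second defence is low stakes. This stands in full: the analysis is exploratory, the SAP defers it, the undisputed resolvins would be reported alongside, and no primary, confirmatory or safety result depends on it.

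Three stronger readings are tempting and should be resisted.

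- A reader might infer that WH 3c contradicts WH 3b, which expects that "a high n-6/n-3 Omega ratio at baseline will be associated with a better response to Omega-3 fatty acids": if HETEs were omega-6 products, a high ratio would suggest high HETE, whereas WH 3c predicts response with low HETE. This does not follow. A ratio is high when n-3 is low even if n-6 is unchanged, and WH 3b itself starts from reduced red-cell EPA and DHA. Nor do the documents link a red-cell fatty acid ratio to the level of an oxidised metabolite.
- A reader might want to express the mismatch as lost power. That needs the correlation between HETEs and the EPA-derived product, and a power for WH 3c. The documents give neither, so any figure would reflect only the values chosen.
- A reader might conclude that WH 3c as a whole uses the wrong markers. The E-series resolvins are not in question.

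**Conclusion.** The point holds as a mismatch between analyte and hypothesis. One of the two marker families in WH 3c does not, by name, measure what the hypothesis is about, and a result for it would be misread as evidence on EPA metabolites. This rests on the protocol's own expansions of the two abbreviations and on ordinary chemical naming. It does not rest on any claim about which fatty acid HETEs do come from, which the documents leave open.

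The size is limited: one marker family, in one exploratory analysis of a listed secondary hypothesis. Sample size, alpha, the resolvin part of WH 3c and the primary CDRS-R analysis are unaffected. It is worth correcting because WH 3c serves the stated objective on response predictors and the plan that will govern it is still to be written under the SAP.

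**What to change.** In Section 5.2 (WH 3c), Section 11.4.1, Section 11.4.3 and the later lipid-marker analysis plan, replace HETEs by HEPEs as the EPA-derived markers, keep the E-series resolvins, and add HEPE to the abbreviation list. If HETEs are still measured, report them separately and not as EPA metabolites, with their parent fatty acid and expected direction stated before assay.

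The cost is wording, plus a few additional targets on the planned LC-MS/MS panel if they are not already included. Timing matters: the synopsis planned the last participant out for 31 March 2022 and the SAP is dated 23 May 2022, so the assay window may already have opened. The documents do not say whether the lipid assays have been run. If they have, the relabelling and separate reporting of HETEs can still be done, but an expected direction set at that stage should be declared as set after assay.

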- **WH4a:** We will test association between pro-inflammatory state and depressive symptoms by calculating Pearson's correlation coefficient or Spearman's correlation coefficient between the severity of symptoms at baseline and the ratio between pro- and anti-inflammatory markers. The same procedure is also applied to omega-6/3 ratio and omega-3 index. To test whether normalization of these parameters will correlate with improvements in depression scores we'll run a linear regression model with depression scores as dependent, and time and pro-inflammatory state, increase in omega-6/3 and omega-3 index as independent variables.
- **WH4b:** We will calculate Pearson's correlation coefficient or Spearman's correlation coefficient of omega-3 index with SIQ-Jr scores depending on the distribution of the data.
- **WH4c:** As above, we will calculate either Pearson's correlation coefficient or Spearman's correlation coefficient (depending on the distribution of the data) between omega-3 index and scores on the IES-27 and overall psychopathology scores.
- **WH4d:** We also test correlations between levels of Omega-3 fatty acids with salvia cortisol, F2 isoprostanes and Connor-Davidsons Resilience Scale scores by

calculating Pearson's correlation coefficient or Spearman's correlation coefficient, respectively.

- **WH5a:** In order to compare treatment groups regarding occurrence of SUSARs, we will run a two proportions z-Test. Differences in suicidal ideation scores are tested by independent t-Test (for normal distributed data) or Mann-Whitney-U-Test (for non-normal data).

The analyses will be performed after closure of the database. The trial statisticians will perform all a-priori defined statistical analyses according to the statistical analyses plan. All other clinical outcome analyses will be declared as post-hoc analysis.

Future analysis based on the BioBank or other add on projects will be subject of an own protocol with separately formulated hypotheses that will be approved the appropriate authorities.

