where time t is considered a factor (while also investigating possibility of linearizing time effect) and randomized treatment group (intervention) and the interaction between randomized treatment group and time are included as fixed effects. The baseline values of the minimization factors age, gender, and hsCRP, as well as baseline antidepressant use and omega-3 index are included as covariates. The baseline outcome measure is modeled in the response, not as a covariate. The terms b_{i0} , b_{i1} , and b_{s0} represent participant-specific random intercepts and slopes and site-specific random intercepts. The random effects are assumed to be normally distributed and an unstructured covariance matrix will be assumed. The error term $\varepsilon_i(t)$ is assumed to be normally distributed with mean zero and variance σ^2 , independent of the random effects and is independent over time. An overall treatment effect for CDRS-R score at 36 weeks ($\beta_1 + \beta_{11}$) will be reported with a 95% confidence interval and corresponding p -value.

The competing survival models for time to event r (intervention dropout or study dropout) take the form:

$$\lambda_{ir}(t) = \lambda_{0r} \exp\{\gamma_1 \text{intervention} + \alpha_r m_i(t)\}$$

where the cause-specific Cox models include intervention as a time-independent effect and the estimated true trajectory of CDRS-R as a time-varying effect. The parameters α_r measure the strength of association between the longitudinal outcome and risk of the corresponding dropout event.

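### Protocol 11.4.3 tests the WH4b–d marker–symptom associations, and the baseline part of WH4a, by raw correlation across ages 8–17 and both genders; the main analysis should be adjusted and use pre-dose values

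*Protocol*

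**What the plan says.** Protocol 5.2 puts WH4b in these terms: "we assume an inverse correlation between Omega-3 fatty acids and suicidal ideation (SIQ-Jr), in particular high levels of EPA will protect against suicidal ideation". Protocol 11.4.3 gives the tests.

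- **WH4b:** "We will calculate Pearson's correlation coefficient or Spearman's correlation coefficient of omega-3 index with SIQ-Jr scores depending on the distribution of the data". Nothing more is specified.
- **WH4c:** the same choice of coefficient, "between omega-3 index and scores on the IES-27 and overall psychopathology scores", again without further detail.
- **WH4d:** "We also test correlations between levels of Omega-3 fatty acids with salvia cortisol, F2 isoprostanes and Connor-Davidsons Resilience Scale scores by" the same two coefficients.
- **WH4a, first part:** the same coefficients between baseline symptom severity and the inflammatory ratio, the omega-6/3 ratio and the omega-3 index. Here the visit is named.

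The distribution of the data is the only stated basis for choosing between Pearson and Spearman. No covariate, stratum or treatment-arm term appears, and WH4b–d name no visit. SAP section 2 leaves marker–symptom relationships to future analysis plans, so Protocol 11.4.3 is the only specification that now exists.

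**The concern.** Randomisation protects comparisons between arms. It does not protect a comparison of children with high and low omega-3 status. Here age and gender are obvious candidates for common causes, and the documents themselves show how they could enter.

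- The study schedule has the self-report block, which contains SIQ-Jr and IES-27, self-rated from 13 years and parent-rated below. Measurement therefore changes with age.
- Protocol 9.2.2.2 describes SIQ-Jr as a version for ages 12–15 that can also be used in younger children.
- Protocol 3.4.4 remarks that depressed males may present with impulsivity and aggression, which bears on the WH4c construct.
- Under Protocol 8.1, children under 13 receive half the capsules. At any post-baseline visit, both age and arm would influence the marker.

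At stake is a reported association between omega-3 status and suicidal ideation in depressed minors that might reflect only who is older, or who did the rating. The wording of WH4b invites a causal reading of it.

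**Working it through.** **No figure to reproduce.** The documents give no sample size, power or expected coefficient for WH4a–d.

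**Where the plan does adjust.** SAP 7.1 puts age, gender and hsCRP in the primary model, "as well as baseline antidepressant use and omega-3 index are included as covariates", and SAP 7.2.1 adjusts its binary and continuous secondary models similarly. Those are randomised comparisons. The non-randomised ones in Protocol 11.4.3 have no adjustment.

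**Inputs for an illustration.**
- From the documents: n = 220 (synopsis) and a two-sided 5% level (Protocol 11).
- Assumed, because the documents give nothing: age correlates with the score at *a* and with the marker at −*b*, and the two have no direct link. Opposite signs are chosen; nothing in the documents supports that choice over equal signs.

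**Formulas.** With no direct link, the raw correlation equals the product of the two age correlations: r = −*ab*. Under the Fisher approximation, let m = atanh(|r|) × √(n − 3), with √217 = 14.73. The rejection rate is 1 − Φ(1.96 − m) + Φ(−1.96 − m).

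| Age–score / age–marker | raw r | m | rejection rate |
|---|---|---|---|
| 0.1 / −0.1 | −0.01 | 0.15 | 5.2% |
| 0.2 / −0.2 | −0.04 | 0.59 | 9.1% |
| 0.3 / −0.2 | −0.06 | 0.88 | 14% |
| 0.3 / −0.3 | −0.09 | 1.33 | 26.5% |

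All these raw values lie below the 0.132 needed for significance at n = 220. The excess rejections come from a shifted centre plus sampling error.

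**Effect of adjustment.** The partial correlation is (r − r₁r₂) / √[(1 − r₁²)(1 − r₂²)], where r₁ and r₂ are the two age correlations. At 0.3 / −0.3 the numerator is −0.09 − (−0.09) = 0. In 10,000 simulated trials of n = 220, the raw test rejected in 9.2% (0.2 / −0.2) and 27.0% (0.3 / −0.3). The age-partial test rejected in 5.0% and 5.3%.

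**Smaller n.** Protocol 9.2.2.4 makes bloods beyond the routine laboratory sample optional. At n = 150 the 9.1% and 26.5% become 7.7% and 19.4%.

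**Same signs.** If both age correlations have the same sign, the product is positive and pulls a genuine inverse correlation towards zero. The same product rule holds for gender as the common cause; no separate figure was computed for it.

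**Timing.** Protocol 9.3.1 has blood, urine and saliva taken before baseline. Protocol 9.3.2 lists the baseline questionnaires after randomisation but before study medication is dispensed. These values are therefore pre-dose, though not strictly pre-randomisation.

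**The case against.** Four arguments limit the point.

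1. **The analyses are deferred.** SAP section 2 reserves them for later plans, which would naturally name covariates and visits. This stands as to timing. It does not remove the gap, because Protocol 11.4.3 and 11.4.6 class analyses not defined in advance as post hoc, so adjustment has to be written down first. Marker assays mostly wait for the last patient's final visit, but Protocol 9.2.2.4 and 11.4 allow earlier use of baseline data.
2. **A related adjusted estimate already exists.** SAP 7.2.2 models SIQ-Jr in the same way as the primary outcome, which brings in omega-3 index, age, gender and a site intercept. This stands in part. That model yields an adjusted index coefficient for SIQ-Jr, but the SAP does not call it the WH4b test. It averages over all visits, conditions on baseline antidepressant use, and does not cover WH4c or WH4d.
3. **The aim is exploratory.** Protocol 3.7 calls the link between suicidal ideation and bioactive lipids more explorative and aimed at characterising subgroups. For describing who is at risk, a raw coefficient is useful. This stands, and is why raw coefficients should be kept as description.
4. **The size is assumed throughout.** This also stands. At correlations of 0.1 there is almost no inflation.

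A reader might also infer that post-baseline visits will be pooled, adding an inverse correlation produced by the capsules. The text names no visit for WH4b–d, but nothing in it proposes pooling.

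**Conclusion.** The gap is real and modest. As written, Protocol 11.4.3 would test non-randomised associations in a sample of mixed age and gender with no control for either, and for WH4b–d at an unspecified visit. Under assumed opposite-sign age correlations of 0.2/0.2 to 0.3/0.3 at n = 220, the 5% test would reject in about 9% to 26% of trials with no direct link. True inflation could be smaller or larger, and the bias could as easily mask an association as create one.

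Two stronger readings are not supported. A reader might infer that the trial is set to report a false protective effect. The documents give no age or gender correlation with either measure, so the direction is unknown, and the word about protection belongs to the hypothesis rather than to a reporting rule. A reader might also infer that the trial's suicidality conclusions are at risk. The SIQ-Jr safety comparison is between randomised arms and is untouched, as are the primary and confirmatory results.

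**What to change.** In Protocol 11.4.3, or in the follow-up biomarker analysis plan that SAP section 2 foresees, and before marker data are analysed:

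- Make one prespecified method the main analysis for WH4b–d and the baseline part of WH4a, for example a partial Spearman correlation.
- Use pre-dose values only: screening blood, urine and saliva, with the baseline-visit score taken before the first dose of randomised capsules.
- Adjust for age, gender and site. Age adjustment carries much of the rater change; state how rater type is handled.
- Put adjustment for baseline antidepressant use in a sensitivity analysis only. Protocol 8.7.1 links prescribing to lack of improvement or worsening, so such use may follow from severity, and conditioning on it can itself introduce bias.
- Keep raw coefficients as descriptive results.
- Report WH4b as an association, and state whether its marker is EPA (the hypothesis) or the omega-3 index (the planned test).

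The cost is a few lines of text. Every covariate is already collected. With age and gender at one degree of freedom each and the seven recruiting sites listed in Protocol section 7 at six, the adjustment uses 1 + 1 + 6 = 8 of about 220.
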